**Phlebotomy:**

Phlebotomy can result in anemia, although the amount of blood taken for these studies should not result in clinically-significant anemia because the blood drawn is spread out over the course of 3 months of participating in the study. Subjects are excluded if hemoglobin < 10 gms/dL or hematocrit of 37 % for males participants and 33 % for female participants.

**10. Minimizing Risks:** Describe the manner in which the above-mentioned risks will be minimized.

General:

- Total blood loss in each subject will be approximately 549 cc over the 3 months of the study if subject completes the entire study (including the optional hyperglycemic clamp portions). Blood draws include: 35 cc at screen, 272 cc at week 0 visit, , and 272 cc at week 12. If the subjects choose not to do the optional hyperclamp portion of the study, the total blood draw will be approximately 202 cc over the course of the study. Blood draws include: 5 cc at screen, 98.5 cc at week 0 visit, , and 98.5 cc at week 12. Subjects with Hgb <10 and hematocrit of 37 % for males participants and 33 % for female participants will be excluded from the study.
- All subjects will be given a telephone number to enable immediate communication with the PI or one of the co-investigators to report any delayed adverse effects.
- Physiological monitoring will be performed during each study.

For glucose infusions:

- Intravenous catheters will be placed under sterile conditions by experienced staff members.
- During glucose infusions, 20% dextrose is used reducing the risk of thrombophlebitis normally associated with the use of excessively hypertonic glucose solutions.
- To avoid hypoglycemia during the overnight insulin infusions, plasma glucose will be monitored closely using a bedside glucose analyzer (YSI). This will involve plasma measurements every 30 minutes and at more frequent intervals if plasma glucose is low (less than 4 mM, 70 mg/dl).
- All studies will be performed under the direct supervision of a physician.
- All solutions for infusion will be pyrogen free and prepared in a sterile environment.

12-week Intensification of Diabetes Regimen:

The 12-week intensification of diabetes management poses minimal risks to the patient. All medical management strategies will follow the general strategies outlined in the Position Statement of the American Diabetes Association and the European Association for the Study of Diabetes [48]. There may be slightly increased risk of hypoglycemia with improved glycemic control; however, as patients are all poorly controlled T2DM patients and we are targeting blood glucose levels to between 80-140 mg/dl before meals and between 100-160 mg/dl at bedtime, we expect that this risk will be minimal. Subjects will be provided with free style libre sensors throughout the study (9 sensors are provided during the 12 weeks that the study last), and free style libre continuous glucose monitor reader. All participants will receive exercise and dietary counseling in accordance with ADA guidelines and increased frequency of medical attention to lower their blood glucose to target ranges. Throughout the study, individuals will be contacted via telephone call or through additional clinic visits as deemed necessary for maintenance of glycemic control. All individuals will receive education regarding the detection and proper management of hypoglycemia.

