15 T2DM subjects and 15 T1DM subjects with chronic hyperglycemia (HbA1C > 7.5%) will participate in a 12-week intervention study aimed at reducing their A1C levels. By lowering their glucose levels, we expect to also decrease activity through the polyol pathway. Subjects will receive exercise and dietary counseling in accordance to guidelines established by the American Diabetes Association. In addition, all patients will have their diabetes regimens adjusted on a weekly basis to achieve a target blood glucose level based upon data from the patients performing self-monitoring of blood glucose (SMGB).

At 0 and 12 weeks, subjects will undergo baseline MRS scan at 4T to measure intracerebral glucose, fructose, and glutathione. Participants may also be invited to participate in an overnight admission to normalize blood glucose levels, and a hyperglycemic clamp. During each of these two scans, plasma glucose, fructose, insulin, HbA1c, and fructosamine levels will be measured concurrently. One week prior to the week 0 and week 12 MRS scans, subjects will be asked to wear a CGMS (Free style libre) to continuously monitor their interstitial blood glucose levels and record their food intake in a food log. After first placing the CGM prior to the week 0 scan, the system is removed after 14 days and then reinserted for 14 days before the week 12 MRS scan.

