All individuals will be asked to perform SMBG at least 4 times a day (before breakfast, lunch, dinner, and bedtime). The daily SMBG records will be sent to [name] weekly for review to guide adjustment of insulin regimens. Target blood glucose levels will be between 80-140 mg/dl before meals and between 100-160 mg/dl at bedtime. Individuals not at goal glycemic targets will undergo intensification of their regimen. Throughout the study, individuals will be contacted via telephone call, email or through additional clinic visits as deemed necessary for maintenance of glycemic control. All individuals will receive education regarding the detection and proper management of hypoglycemia.

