**Optional Hyperglycemic clamp:**

Prior to MRS scanning at weeks 0 and 12 Subjects may also be invited to participate in an optional overnight admission to normalize blood glucose levels the night before scanning and then a hyperglycemic clamp the following morning.

Subjects will be admitted in the evening prior to MRS scan day (~ 6 PM) to the YNHH research unit, all of their diabetic medications will be held and they will be placed on an insulin drip beginning at 8PM to maintain blood sugar levels at ~90-100 mg/dl until 7AM the next morning. The next morning, participants will be taken to the MRRC for MRS scanning. Following the 45 minute

baseline scan, subjects will remain in the scanner for continuous scanning during the hyperglycemic clamp (see figure). An infusion of 20% dextrose at a variable rate to maintain plasma glucose levels at 220 mg/dL for 4 hours. Glucose infusion rates will be adjusted in response to plasma glucose levels measured every 5-10 minutes. Subjects will be able to take breaks as needed during the 3 hours hyperglycemic clamp and MRS scan. At baseline, 2 and 4 hours, plasma samples will also be obtained for fructose, sorbitol, insulin levels and other hormonal markers.

**Continuous glucose monitoring system (CGMS) and Food logs (at -1, and 11 weeks):** One week prior to the MRS scans at 0 and 12 weeks, subjects will be asked to wear a CGMS (Free style libre) to continuously monitor their interstitial blood glucose levels and record their food intake

**Blood collection for platelet and inflammation analysis:** Participants will also have blood collected (~80 cc) for analysis of polyol pathway activity in platelets as well as for changes in inflammatory markers such as cytokines IL-6, TNF-alpha at weeks 0, and 12 weeks.

**Optional Specimens for Future Storage:** Subjects will be asked to give permission for the storage of any blood obtained during the study that will not be used for the above noted analysis

**4. Genetic Testing** N/A

**5. Subject Population:** Provide a detailed description of the types of human subjects who will be recruited into this study.

15 T2DM subjects with HbA1C > 7.5%

15 T1DM subjects with HbA1C > 7.5%

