- Recruitment through JDAT: The Joint Data Analytics Team (JDAT) will also be used to query eligible patients in EPIC based on the eligibility criteria. JDAT will also be used to identify potential subjects with the various permutations of diagnosis codes related to type 2 diabetes. JDAT will identify and send a study communication to potential participants based on these criterion that fall within the following time period: the last 2 years. Potential participants who do not use MyChart will receive a paper mailing including information about the study. JDAT will not identify the potential participants to the researchers, and therefore the researchers will receive no identifiable information from JDAT.
- Messaging to Study Participants: The following wording will be used in the letter or MyChart message patients receive via JDAT describing the study and inviting them to participate:

“You are receiving this [MyChart message or this letter] because you were diagnosed with type 1 or type 2 diabetes. You may be eligible to participate in a diabetes research study conducted by Yale University investigators to better understand the role of sugar in the brain. . The Yale New Haven Health electronic health record system has searched medical conditions to find people who may be good matches for research studies. No one has looked at your record and no information has been shared with any research doctor or research team member. Just because you received this message does not mean that you are in a research study or that you have to decide to be in this or any study. To opt-out of research, including opting out of receiving future messages about research studies, please email [[contact]](mailto:[contact]) or call [name] and select option #3.”

The message/mailing will also include the following consent information:

“You are invited to take part in a research study designed to look at the role of sugar in the brain. Approximately 30 subjects with diabetes (type 1 and type 2) will be enrolled in this study. The study involves 12 weeks of one-on-one diabetes management with an endocrinologist with the goal of improving your diabetes control. It involves a screening history, physical exam, blood work, and MRI scans of your brain while blood sugar levels are adjusted. Participants will also receive exercise and dietary counseling and will be provided with the FreeStyle Libre continuous glucose monitor (CGM) during their time in the study”.

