## SECTION X: RESEARCH ALTERNATIVES AND ECONOMIC CONSIDERATIONS

1. **Alternatives:** What other alternatives are available to the study subjects outside of the research? The alternative is to decline participation in the study.
2. **Payments for Participation (Economic Considerations):** Describe any payments that will be made to subjects, the amount and schedule of payments, and the conditions for receiving this compensation.

\$25 for the screening visit

\$50 for wearing the CGMS at week -1

\$150 for overnight admission/Hyperglycemic clamp/MRS scans at week 0 (Optional)

\$50 for wearing the CGMS at week 11

\$325 for overnight admission/Hyperglycemic clamp/MRS scans at week 12 (Optional)

Payments will be given via a Bank of America pre-paid debit card using the new Yale electronic payment service. After the first payment milestone (first study visit) subjects will receive a card in the mail which will need to be activated over the phone, any subsequent milestones

payments will automatically add additional funds to the subject's card. Reimbursement for incidental expenses will also be provided.

**3. Costs for Participation (Economic Considerations):** Clearly describe the subject's costs associated with participation in the research, and the interventions or procedures of the study that will be provided at no cost to subjects.

The medical evaluation including physical examination and study related laboratory work will be performed at no additional cost to the study participant.

**4. In Case of Injury:** This section is required for any research involving more than minimal risk.

- a. Will medical treatment be available if research-related injury occurs?
- b. Where and from whom may treatment be obtained?
- c. Are there any limits to the treatment being provided?
- d. Who will pay for this treatment?
- e. How will the medical treatment be accessed by subjects?

Medical treatment will be offered to the subjects for any physical injuries that they receive because of participating in this research. Yale School of Medicine and Yale-New Haven Health does not provide funds for treatment of research-related injury. However, the subject or his/her insurance company is responsible for the cost. Federal regulations require that subjects be told that if they are physically injured, no additional financial compensation is available. Subjects do not give up any legal rights by signing the consent form.

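### CGM wear is scheduled two incompatible ways, overnight CGM data have no stated place in the weekly regimen review, and the hypoglycemia rationale leaves out the type 1 half of the sample

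*Combined protocol and SAP*

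**What the plan says.** All references are to the Combined protocol and SAP.

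**Two-window wear.** The study summary in Section V, item 1 (Statement of Purpose) has the sensor placed one week before the week 0 scan, after which "the system is removed after 14 days and then reinserted for 14 days before the week 12 MRS scan". The Research Plan (Section V, item 3) heads its paragraph "Continuous glucose monitoring system (CGMS) and Food logs (at -1, and 11 weeks". Section X, item 2 pays for wear in week -1 and again "for wearing the CGMS at week 11".

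**Supply throughout.** Section V, item 10 (Minimizing Risks), in the paragraph on the 12-week intensification, states: "Subjects will be provided with free style libre sensors throughout the study (9 sensors are provided during the 12 weeks that the study last". It adds a reader for the subject. The recruitment message in Section VII, item 3 says that participants "will be provided with the FreeStyle Libre continuous glucose monitor (CGM) during their time in the study".

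**Data used to adjust treatment.** Section V, item 1 adjusts regimens "based upon data from the patients performing self-monitoring of blood glucose (SMGB". The Research Plan asks subjects to "perform SMBG at least 4 times a day (before breakfast, lunch, dinner, and bedtime" and sends those records "weekly for review to guide adjustment of insulin regimens".

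**Risk reasoning.** Section V, items 9 and 10 expect hypoglycemia risk to be minimal, partly because every participant is described as a type 2 patient in poor control. Section V, item 7 enrols 15 type 1 and 15 type 2 subjects.

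**The concern.** Staff reading this plan cannot tell whether a subject should be wearing a sensor through the middle of the intensification period. That is when regimens are being tightened toward 80 to 140 mg/dl before meals. The scheduled fingerstick times include none overnight, so without a sensor nothing scheduled records glucose during the night. If the removal clause is followed, most of the sensors supplied go unused. Even if sensors are worn throughout, no section says that the endocrinologist adjusting the regimen looks at the overnight trace.

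The written reason for calling the hypoglycemia risk minimal does not cover the type 1 subjects, who are half the sample. It needs correcting whichever wear schedule was intended.

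There is also an analysis reason to settle the schedule: CGM measures of glycemia are part of primary endpoint (a) in Section V, item 12.

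**Working it through.** **Inputs from the documents.** Intensification lasts 12 weeks: 12 × 7 = 84 nights, day 0 to day 84. The first sensor goes on at day -7 and comes off after 14 days (item 1). The second wear is given both as 14 days before the week 12 scan and as starting one week before it (item 1). Nine sensors are supplied (item 10). There are 30 subjects, 15 of them type 1 (item 7).

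**Assumption.** Each sensor lasts 14 days. This is taken from the wear period in item 1; no sensor life is stated.

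**The plan's own figure, 9 sensors.** No derivation is given, so only its fit can be tested, using sensors needed = days ÷ days per sensor, rounded up.
- Two 14-day windows: 28 / 14 = 2, leaving 7 of 9 unused.
- Continuous, day 0 to 84: 84 / 14 = 6.
- Continuous, day -7 to 84: 91 / 14 = 6.5, so 7.

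Nine is enough for continuous wear and far more than two windows need.

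**Nights without a CGM record if item 1 governs.**
- First removal: -7 + 14 = day 7.
- Second wear 14 days before the scan: starts 84 - 14 = day 70. Gap 70 - 7 = 63 nights; 63 / 84 = 75%.
- Second wear one week before the scan: starts 84 - 7 = day 77. Gap 77 - 7 = 70 nights; 70 / 84 = 83%.
- Over 30 subjects: 30 × 63 = 1,890 to 30 × 70 = 2,100 subject-nights. In type 1: 15 × 63 = 945 to 15 × 70 = 1,050.

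If the Research Plan paragraph is read alone, as seven days of wear before each scan and nothing else, the gap is 84 - 7 = 77 nights.

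**If item 10 describes actual wear:** the gap is 0 nights.

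**Overnight data in the weekly review.** The named fingerstick times are three pre-meal readings and one at bedtime. The records named for weekly review are these readings. CGM data are not named there, under either schedule.

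**Sensitivity to sensor life.** Nine sensors cover 91 days if each lasts at least 91 / 9 = 10.1 days. If the first sensor must come off at the week 0 scan, 14-day wear needs 1 + 84 / 14 = 7 sensors. In that case the 8 remaining sensors must each last at least 84 / 8 = 10.5 days.

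**Review time (assumed 2 to 10 minutes per subject per week).** 30 × 12 = 360 subject-weeks; 360 × 2 / 60 = 12 hours; 360 × 10 / 60 = 60 hours. At 5 minutes it is 30 hours.

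**The case against.** The strongest reply is that the two descriptions serve different purposes. Weeks -1 and 11 would be the research measurement and payment windows, and the nine sensors would be clinical supply worn throughout. On that reading the Research Plan heading and the payment schedule contradict nothing, only the removal clause in the summary is wrong, and the gap is zero. The sensor count makes this plausible. What remains is that no section states this reading and that the removal and reinsertion clause contradicts it, so the wording still needs repair.

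The existing safeguards are also real: fingersticks at least four times a day, a bedtime target of 100 to 160 mg/dl, weekly review, hypoglycemia education, calls or extra visits as needed, and a telephone number for immediate contact.

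The documents do not support several stronger readings that a reader might infer:
- **That the CGM record reaches nobody, or plays no part in detecting lows.** Subjects hold a reader, supplied in the same paragraph that discusses hypoglycemia, and nothing excludes clinician review. The supportable statement is that such review is not stated.
- **That the recruitment message independently promises continuous wear.** It mentions neither sensors nor a count and could fit intermittent wear. The conflict rests on item 10 against item 1.
- **That insulin rises every week in everyone.** Regimens are adjusted weekly, the Research Plan intensifies only subjects not at goal, and eligibility does not require type 2 subjects to use insulin.

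**Conclusion.** The wording conflict between Section V, items 1 and 10 is real, and the risk sentence in items 9 and 10 is wrong for 15 of 30 subjects. The gap of 63 to 70 of 84 nights holds only if the removal clause governs wear; on the other plausible reading it is zero. Clinician review of overnight CGM data is unstated under both.

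The night counts measure time without a record. They should not be read as an estimate of missed hypoglycemia: the documents give no rate of lows, so none can be derived. Item 10 promises supply and does not order nightly wear, so the change adds a modest safeguard and does not restore one already defined. It merits consideration as a cheap safety improvement. The sensor arithmetic rests on 14-day wear, and the review hours on assumed minutes.

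**What to change.** 1. In Section V, item 1, replace the removal and reinsertion clause with continuous wear from week -1 to the week 12 scan for all 30 subjects, and align the CGM paragraph in item 3. Keep the pre-scan periods as the endpoint measurement windows; the payments in Section X can stay tied to them.
2. State what happens at the scanner. Items 9 and 10 require metal objects to be removed before the magnet area, so say that a sensor is taken off beforehand and replaced afterwards if MRI safety rules require it.
3. In the intensification paragraphs of item 3, add that available CGM data are checked for overnight lows whenever the regimen is adjusted.
4. Rewrite the hypoglycemia risk sentence in items 9 and 10 so that it covers type 1 diabetes.

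**Cost.** No change to visits, sample size or endpoints. Sensor need is 6 (84 days) to 7 (91 days, or with a change at the week 0 scan) of the 9 supplied, at 14-day wear. Against two windows that is 6 - 2 = 4 to 7 - 2 = 5 more insertions per subject, with the minor site risks listed in item 9. The CGM check is a new step for the clinician, an assumed 12 to 60 hours over the whole study, and lows seen on the trace may occasionally delay an insulin increase.

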**MRI/MRS:**

- Subjects and all personnel are required to fill out an MRI safety questionnaire to ensure safety. Also, all subjects are scanned with a metal detector before entering the magnet area and all metal objects are removed.
- Subjects with metal implants or pacemakers are not admitted to this study.
- Some subjects feel claustrophobic or experience physical discomfort inside the scanner. Communication is set up so that the subjects can talk to the investigators and may be removed from the scanner if they are uncomfortable.
- A RN will be present inside the scanner at all times with the subject.
- 

**Breach of Confidentiality:** It is possible that an unauthorized individual may gain access to subjects private information. We will make every effort to keep the data safe and private. For more information about how your data is protected, review the “Confidentiality and Security of Data paragraph on page 23.

**11. Data and Safety Monitoring Plan:** Include an appropriate Data and Safety Monitoring Plan (DSMP) based on the investigator's risk assessment stated below. (Note: the HIC will make the final determination of the risk to subjects.) For more information, see the Instructions, page 24.

- a. What is the investigator's assessment of the overall risk level for subjects participating in this study? **Greater than minimal/moderate**
- b. If children are involved, what is the investigator's assessment of the overall risk level for the children participating in this study? N/A
- c. Copy, paste, and then tailor an appropriate Data and Safety Monitoring Plan from <http://www.yale.edu/hrpp/forms-templates/biomedical.html> for
  - i. Minimal risk
  - ii. Greater than minimal/moderate risk
  - iii. High risk
- d. For multi-site studies for which the Yale PI serves as the lead investigator: N/A

### **MODERATE RISK DSMP**

**Personnel responsible for the safety review and its frequency:**

The principal investigator will be responsible for monitoring the data, assuring protocol compliance, and conducting the safety reviews at the specified frequency which must be conducted at a minimum of every 6 months (including when reapproval of the protocol is sought). During the review process, the principal investigator (monitor) will evaluate whether the study should continue unchanged, require modification/amendment, or close to enrollment. Either the principal investigator, the IRB, or MRRC have the authority to stop or suspend the study or require modifications.

**The risks associated with the current study are deemed moderate for the following reasons:**

Although we have assessed the proposed study as one of moderate risk, the potential exists for anticipated and/or unanticipated adverse events, serious or otherwise, to occur since it is not possible to predict with certainty the absolute risk in any given individual or in advance of first-

hand experience with the proposed study methods. Therefore, we provide a plan for monitoring the data and safety of the proposed study as follows:

